4.2 SCIENTIFIC RATIONALE FOR STUDY DESIGN

Based on histology, therapy and prognosis, lung cancer is divided into two major classes: small-cell lung cancer (SCLC) and non-small-cell lung cancer (NSCLC). NSCLC accounts 80% of lung cancer and it includes 2 major subtypes: non-squamous carcinoma (including adenocarcinoma, large-cell carcinoma and other subtypes) and squamous cell (epidermoid) carcinoma. Adenocarcinoma is the most common subtype of NSQ-NSCLC (17).

The past decade has dramatically changed the approach on diagnosis and treatment of lung cancer with the concept of personalized medicine, which led discovery of several therapeutic

options that are only approved for treatment of patients with specific histopathologic characteristics (22).

Accurate pathologic assessment with tumor mutation profiling and staging are essential for treatment decisions. In general, systemic therapy is recommended for patients with metastatic (Stage IV) disease, especially in disseminated metastasis. Appropriate systemic therapy choice depends on the histologic type, whether there are genetic alterations that can be targeted for therapy, and the performance status of the patient.

In the advanced setting, platinum-based chemotherapy has been considered the gold standard, with evidence of improved survival and symptom control, and superior quality of life compared to best supportive care. After improvement of biomarker testing for genetic alterations in tumor cells, the number of available targeted therapies has been increasing, and targeted therapy has been shown to decrease tumor burden, decrease symptom and dramatically improve the quality of life for patient with specific genetic alteration.

Doublet chemotherapy regimens are recommended as first line chemotherapy for NSQ NSCLC patients whose tumor has negative *ALK* and *ROS1* re-arrangement or sensitizing *EGFR* mutations and with PD-L1 expression <50% or unknown. Based on genetic profiling, targeted therapies maybe considered as first line before or as second line therapy after platinum-based chemotherapy.

Immune-checkpoint inhibitors are recommended as subsequent therapy for all patients, based on reported improvement in survival, longer response duration, and a better safety profile compared to chemotherapy. Current data suggest that patients with *EGFR* mutations or *ALK* rearrangement have low response rates to PD-1 or PD-L1 inhibitors when compared to patients without these alterations; therefore checkpoint inhibitors are not considered as recommended subsequent treatment in patients with these alterations.

Since ramucirumab has shown activity in combination with docetaxel in the REVEL study (7), it is anticipated that ramucirumab combined with tusamitamab ravtansine should also show antitumor activity in advanced NSQ NSCLC. Due to the different mechanisms of action of tusamitamab ravtansine and ramucirumab, their combination should have better efficacy than either agent alone, and based on lack of anticipated PK interaction, should have similar safety profiles to those with either monotherapy. Because tusamitamab ravtansine's safety profile differs from that of docetaxel, it is expected that the safety of a ramucirumab/tusamitamab ravtansine combination will be improved compared to the combination of ramucirumab with docetaxel currently approved to treat advanced NSCLC.

4.3 DOSE JUSTIFICATION

In the dose-escalation phase of first-in-human study TED13751 exploring 5 to 150 mg/m² tusamitamab ravtansine doses administered once every 2 weeks, the recommended dose was determined to be 100 mg/m² administered every 2 weeks. A cohort of patients with heavily pretreated, CEACAM5-positive, NSQ NSCLC ongoing in TED13751 are receiving tusamitamab ravtansine at the recommended dose of 100 mg/m² every 2 weeks. Results from the 64 treated and evaluable patients from this cohort showed encouraging antitumor activity in the subset with NSQ

NSCLC tumors that were $\geq 50\%$ positive for CEACAM5 expression (6). This antitumor activity was associated with a response rate of 20.3% (95% CI, 12.3% to 31.7%) per RECIST v1.1 in the response-evaluable population.

As no overlap in the safety profiles for ramucirumab and for tusamitamab ravidansine is anticipated, the starting dose tested in the Part 1 of the study for tusamitamab ravidansine will be the MTD used in monotherapy, 100 mg/m² every 2 weeks. In the event of a safety concern, the dose will be decreased to 80 mg/m² every 2 weeks. Should a safety concern still exist despite a decrease in the dose, the study will be definitively stopped.

A fixed dose of ramucirumab will be administered. The dosage chosen for ramucirumab of 8 mg/kg Q2W has been approved as monotherapy for the treatment of pretreated hepatocellular carcinoma; as monotherapy or in combination with paclitaxel for the treatment of heavily pretreated advanced or metastatic gastric or gastroesophageal-junction adenocarcinoma; and in combination with FOLFIRI for the treatment of CRC. Therefore, extensive postmarketing clinical experience as well as registrational trials for these indications demonstrate both acceptable safety and tolerability of the 8 mg/kg Q2W regimen in heavily pretreated patients with advanced cancers, as well as potent antitumor activity. Because nonclinical studies do not predict an effect of tusamitamab ravidansine on ramucirumab metabolism or exposures, it is not anticipated that any adjustment to ramucirumab dosing will be required for the combination.

Combining ICI and VEGF/VEGF receptor inhibition have shown benefit in multiple tumor types through immune modulation. Pembrolizumab 200 mg iv and ramucirumab 10mg/kg every 3 weeks (P+R) were evaluated in patients with advanced, ICI-exposed, in a substudy of Lung-MAP1, a master protocol for patients with Stage IV previously treated NSCLC. In this randomized, Phase II study from the Lung-MAP platform, 136 patients were randomized to receive pembrolizumab + ramucirumab or the Investigator's choice of standard therapeutic regimens (SOC). Overall survival (OS) was significantly improved with P+R compared to SOC: median (95% CI) OS was 14.5 (13.9 to 16.1) months for P+R: and 11.6 (9.9 to 13.0) months for SOC (HR: 0.69 [0.51 to 0.92], P value from the standard log-rank test equal to 0.05 and 0.15 from the weighted log-rank test). Neither progression-free survival (PFS) or objective response rate (ORR) differed between the treatment arms (2).

As of August 2022, a total of 20 patients were treated in the ACT16146 study. Preliminary encouraging signs of activity with the 3 regimens - tusamitamab ravidansine (SAR408701) combined with pembrolizumab and platinum-based chemotherapy with or without pemetrexed, have been observed. The combination of tusamitamab ravidansine with pembrolizumab, with or without chemotherapy, is feasible and well tolerated without new safety signal observed. Given the development of a dose limiting toxicity with 170 mg/m² and the association between exposure and development of ocular toxicity observed in first-in-human (FIH) study, as well as a lack of discernable difference in efficacy between 150 and 170 mg/m², 150 mg/m² has been chosen as the recommended dose for tusamitamab ravidansine in subsequent studies when combined with pembrolizumab with or without chemotherapy.

The starting dose for tusamitamab ravidansine is 150 mg/m² and was defined based on findings from first-in-human study TED13751. In this study, the RP2D for tusamitamab ravidansine given Q3W was 170 mg/m². Given that tusamitamab ravidansine exposure PK parameters at Cycle 1 of

administration as a single agent of 170 mg/m² Q2W were significantly associated with the occurrence of Grade ≥ 2 corneal events, it is anticipated that 150 mg/m² may result in less ocular toxicity, and overall will be better tolerated than 170 mg/m². In addition, this dose corresponds to the same dose intensity as with the recommended 100 mg/m² Q2W dose.

Based on the experience of the first patients treated in ACT16146 for the dosage of tusamitamab ravtansine and pembrolizumab and the experience of the doublet cohort, the starting dose for tusamitamab ravtansine will be 150 mg/m², ramucirumab 10 mg/kg and pembrolizumab 200 mg, every 3 weeks.

4.4 END OF STUDY DEFINITION

A participant is considered to have completed the study if he/she has completed all phases of the study including the End of Treatment visit and the Follow-Up visit approximately 90 days after the last IMP administration. The end of the study is defined as the date of the last visit of the last participant in the study, or last scheduled procedure shown in the Schedule of Activities for the last participant in the trial globally.

5 STUDY POPULATION

Prospective approval of protocol deviations from recruitment and enrollment criteria, also known as protocol waivers or exemptions, is not permitted.

5.1 INCLUSION CRITERIA

Participants are eligible to be included in the study only if all the following criteria apply:

Age

I 01. Participants must be ≥ 18 years of age (or country's legal age of majority, if >18 years), at the time of signing the informed consent.

Type of participant and disease characteristics

I 02. Histologically or cytologically proven diagnosis of NSQ NSCLC.

I 03. Metastatic disease progression fulfilling both of the following 2 criteria:

a) Having progressive disease during or after platinum-based chemotherapy (at least 2 cycles). Maintenance therapy following platinum-based chemotherapy is not considered as a separate regimen. Adjuvant/neoadjuvant treatment for a patient who had a relapse with metastatic disease during or within 6 months of completing treatment will be considered as first-line treatment.

AND

b) Having progressive disease during or after 1 immune checkpoint inhibitor (anti-PD1/PD-L1); this could be given as monotherapy or in combination with platinum-based chemotherapy (whatever the order).

I 04. For a tumor genotype with a sensitizing *EGFR* mutation or *BRAF* mutation or *ALK/ROS* alteration, demonstrated disease progression while receiving approved treatment for that genotype in addition to platinum-based chemotherapy and immune checkpoint inhibitor.

I 05. Expression of *CEACAM5* as demonstrated prospectively by a centrally assessed immunohistochemical (IHC) assay of $\geq 2+$ in intensity involving at least 50% of the tumor cell population in archival tumor sample (or if not available fresh biopsy sample). At least 5 slides of formalin-fixed, paraffin embedded (FFPE) tumor tissue sectioned at a thickness of 4 μ m are required. If less material is available, the patient could still be considered eligible after discussion with the Sponsor, who may assess and confirm that the available material is sufficient for key evaluations.

I 06. At least one measurable lesion by RECIST v1.1 as determined by local site Investigator radiology assessment. An irradiated lesion can be considered measurable only if progression has been demonstrated on the irradiated lesion.

I 07. Eastern Cooperative Oncology Group (ECOG) performance status 0-1.

Sex

I 08. All (male or female)

Contraceptive use by men or women should be consistent with local regulations regarding the methods of contraception for those participating in clinical studies.

a) Male participants

A male participant must agree to use contraception (see Appendix 5, [Section 10.5](#)) during the intervention period and for at least 4 months after the last dose of study intervention.

b) Female participants

A female participant is eligible to participate if she is not pregnant (see Appendix 5, [Section 10.5](#)), not breastfeeding, and at least 1 of the following conditions applies:

- Not a woman of child-bearing potential (WOCBP) as defined in Appendix 5 ([Section 10.5](#)).

OR

- A WOCBP who agrees to follow the contraceptive guidance in Appendix 5 ([Section 10.5](#)) during the intervention period and for at least 7 months after the last dose of study intervention.

Informed Consent

I 09. Capable of giving signed informed consent which includes compliance with the requirements and restrictions listed in the informed consent form (ICF) and in this protocol.

5.2 EXCLUSION CRITERIA

Participants are excluded from the study if any of the following criteria applies:

Medical conditions

E 01. Untreated brain metastases and history of leptomeningeal disease. Patients with previously treated brain metastases may participate provided they are stable (ie, without evidence of progression by imaging for at least 4 weeks prior to the first administration of study intervention, and any neurologic symptoms have returned to baseline); there is no evidence of new or enlarging brain metastases; and the patient does not require any systemic corticosteroids to manage brain metastases within 3 weeks prior to the first dose of study intervention.

E 02. Significant concomitant illness, including any severe medical condition that, in the opinion of the investigator or Sponsor, would impair the patient's participation in the study or interpretation of the results.

- E 03. History within the last 3 years of an invasive malignancy other than that treated in this study, with the exception of resected/ablated basal or squamous-cell carcinoma of the skin or carcinoma in situ of the cervix, or other local tumors considered cured by local treatment.
- E 04. History of known acquired immunodeficiency syndrome (AIDS)-related illnesses or known human immunodeficiency virus (HIV) disease requiring antiretroviral treatment; or active infection with hepatitis A, B (defined as either positive HBs antigen or positive hepatitis B viral DNA test above the lower limit of detection of the assay), or C (defined as known positive result for antibodies to hepatitis C and known quantitative hepatitis C virus [HCV] RNA results greater than the lower limit of detection of the assay).
- E 05. Non-resolution of any prior treatment-related toxicity to < Grade 2 according to NCI CTCAE V5.0, with the exception of alopecia, vitiligo, or active thyroiditis controlled with hormone replacement therapy.
- E 06. Unresolved corneal disorder or any previous corneal disorder considered by an ophthalmologist to predict higher risk of drug-induced keratopathy. The use of contact lenses is not permitted. Patients using contact lenses who are not willing to stop wearing them for the duration of the study intervention are excluded.
- E 07. Radiographic evidence of major airway or blood vessel invasion or intratumor cavitation, regardless of tumor histology.
- E 08. History of uncontrolled hereditary or acquired arterial thrombotic disorder or history of aneurism.
- E 09. Major surgery within 28 days prior to Day 1/first IMP infusion, or subcutaneous venous access device placement within 7 days prior to Day1. Postoperative bleeding complications or wound complications from a surgical procedure performed in the last 2 months.
- E 10. History of gross hemoptysis (defined as bright red blood or $\geq 1/2$ teaspoon or ≥ 2.5 mL) within 2 months before the first administration of study intervention.
- E 11. Clinically relevant congestive heart failure (CHF; NYHA II-IV, or LVEF less than 50%) or symptomatic or poorly controlled cardiac arrhythmia.
- E 12. Any arterial thrombotic event, including myocardial infarction, unstable angina, cerebrovascular accident, or transient ischemic attack, within 6 months before the first administration of study intervention.
- E 13. Uncontrolled arterial hypertension (systolic ≥ 150 mmHg or diastolic ≥ 90 mmHg) despite standard medical management. A participant with systolic pressure >150 mmHg or diastolic pressure >90 mmHg is ineligible for the study.
- E 14. Serious or nonhealing wound, skin ulcer, or bone fracture within 28 days before the first administration of study intervention.

- E 15. Gastrointestinal (GI) perforation and/or fistulae within 6 months prior to first administration of study intervention.
- E 16. Significant bleeding disorders, vasculitis, or Grade 3-4 gastrointestinal (GI) bleeding within 3 months before the first administration of study intervention.
- E 17. Bowel obstruction, history or presence of inflammatory enteropathy or extensive intestinal resection Crohn's disease, ulcerative colitis, or chronic diarrhea.
- E 18. Medical condition requiring concomitant administration of a medication with a narrow therapeutic window and metabolized by CYP₄₅₀ (See Appendix 9, [Section 10.9](#)); and for which a dose reduction cannot be considered.
- E 19. Medical conditions requiring concomitant administration of a strong CYP3A inhibitor (see Appendix 10; [Section 10.10](#)), unless it can be discontinued at least 2 weeks before first administration of study intervention.

Prior/concomitant therapy

- E 20. Concurrent treatment with any other anticancer therapy.
- E 21. More than 1line previous chemotherapy in metastatic setting.
- E 22. Prior treatment with ramucirumab or docetaxel.
- E 23. Prior therapy targeting CEACAM5.
- E 24. Prior maytansinoid treatment (DM1 or DM4 antibody-drug conjugate).
- E 25. Washout period before the first administration of study intervention of less than 3 weeks or less than 5 times the half-life, whichever is shorter, for prior antitumor therapy (chemotherapy, targeted agents, immunotherapy and radiotherapy, or any investigational treatment).
- E 26. Contraindication to use of corticosteroid premedication.
- E 27. Current therapeutic anticoagulation with warfarin, low-molecular-weight heparin, or similar agents. Patients receiving prophylactic, low-dose anticoagulation therapy are eligible provided that the coagulation parameters defined in the inclusion criteria (INR \leq 1.5 or PT \leq 1.5 \times ULN, and PTT/aPTT \leq 1.5 \times ULN) are met.

Prior/concurrent clinical study experience

- E 28. Previous enrollment in this study, current participation in any other clinical study involving an investigational study treatment, or any other type of medical research.

Diagnostic assessments

E 29. Poor organ function as defined by any one of the following prior to IMP administration:

- a) Serum creatinine $>1.5 \times$ upper limit of normal (ULN) or 1.0 to $1.5 \times$ ULN with estimated glomerular filtration rate (eGFR) $<60 \text{ mL/min}/1.73 \text{ m}^2$ as estimated using a Modification of Diet in Renal Disease (MDRD) formula.
- b) Total bilirubin $>1.0 \times$ ULN.
 - aspartate aminotransferase (AST), alanine aminotransferase (ALT) $>2.5 \times$ ULN or
 - AST, ALT $>5 \times$ ULN in case of documented liver metastasis
 - or
 - AST, ALT $>1.5 \times$ ULN concomitant with alkaline phosphatase (ALP) $>2.5 \times$ ULN. ALP $>5 \times$ ULN with normal ALT/AST, for patients with bone metastases.
- c) Neutrophils $<1.5 \times 10^9/\text{L}$
 - or
 - platelet count $<100 \times 10^9/\text{L}$
 - or
 - hemoglobin $<9 \text{ g/dL}$ (blood infusion-free for at least 2 weeks).

E 30. Urine dipstick or routine analysis indicating proteinuria of 2+ or higher, unless a 24 hour urine collection demonstrates $<1000 \text{ mg}$ of protein.

Other exclusions

- E 31. Individuals accommodated in an institution because of regulatory or legal order; prisoners or subjects who are legally institutionalized.
- E 32. Any country-related specific regulation that would prevent the subject from entering the study - see Appendix 8: Country-specific requirements ([Section 10.8](#)).
- E 33. Participant not suitable for participation, whatever the reason, as judged by the Investigator, including medical or clinical conditions, or participants potentially at risk of noncompliance to study procedures.
- E 34. Participants are dependent on the Sponsor or Investigator (in conjunction with Section 1.61 of the ICH-GCP Ordinance E6).
- E 35. Participants are employees of the clinical study site or other individuals directly involved in the conduct of the study, or immediate family members of such individuals.
- E 36. Any specific situation during study implementation/course that may rise ethics considerations.
- E 37. Sensitivity to any of the study interventions, or components thereof, or drug or other allergy that, in the opinion of the Investigator, contraindicates participation in the study.

Triplet cohort exclusions

- E 38. History of active autoimmune disease that has required systemic treatment in the past 2 years.
- E 39. History of allogeneic tissue/solid organ transplantation.
- E 40. Active infection requiring IV systemic therapy within 2 weeks prior to first study intervention administration or active tuberculosis.
- E 41. Interstitial lung disease or history of pneumonitis that has required oral or IV steroids.
- E 42. Symptomatic herpes zoster within 3 months prior to screening.
- E 43. Significant allergies to humanized monoclonal antibodies.
- E 44. Any radiation therapy to lung >30 Gy within 6 months of first study intervention administration.
- E 45. Has received or will receive a live vaccine within 30 days prior to the first study intervention administration.
- E 46. Thyroid-stimulating hormone (TSH) out of normal limits. If TSH is not within normal limits at baseline, the subject may still be eligible if T3 and free T4 are within the normal limits

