- h Hematology: Hemoglobin, hematocrit, RBC, WBC with differential, platelet counts. These tests will be done before IMP administration at each cycle. If Grade 4 neutropenia, assess absolute neutrophil count (ANC) every 2-3 days until ANC $\geq 0.5 \times 10^9/L$. During first 2 cycles, hematology will be performed weekly.
- i Coagulation: International normalized ratio (INR), aPTT.
- j Clinical blood chemistry: Liver function tests: SGOT (AST), SGPT (ALT), total bilirubin, conjugated bilirubin, AP. Renal function tests: Urea (or BUN) & creatinine. Electrolytes: Sodium, potassium, calcium, glucose. Others: LDH, albumin and total proteins. During first cycle, liver function tests will be performed weekly. The liver function tests and renal function tests will be done before IMP administration at each cycle, unless clinically appropriate. In case of Grade ≥ 3 liver function abnormal tests, additional tests will be repeated every 2-3 days until recovery to baseline value.
- k Urinalysis tests on morning spot will be performed by dipstick at baseline, and at every treatment cycle. In case of proteinuria $\geq ++$ (dipstick), proteinuria quantification by proteinuria/24 h should be performed.
- l Serum pregnancy test: women of childbearing potential must have a negative serum pregnancy test result within 7 days prior to the initial dose of IMP. A pregnancy test (serum/urine) will be repeated every 4 weeks before IMP administration, and a serum test will be repeated at the End of Treatment evaluation (30 \pm 5 days after the last IMP administration), and at the Follow-up visit (90 \pm 7 days after last IMP dose).
- m Echocardiogram or MUGA scan: left ventricular ejection fraction (LVEF) will be evaluated during screening period, and whenever clinically indicated.
- n 12-lead ECG is required at baseline (In case the ECG performed less than 7 days before 1st IMP administration is considered as normal, there is no need to repeat it just before the 1st IMP) before starting the and after completing the first IMP administration (within 30 minutes after the end of tusamitamab ravtansine infusion). The ECG after the infusion at cycle1 should be performed at any case; before IMP administration at each cycle; and at the End of treatment evaluation, 22 to 30 days after last IMP administration.

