Ramucirumab is an antiangiogenic therapy and has the potential to increase the risk of severe bleeding. Permanently discontinue ramucirumab in patients who experience severe (Grade 3 or Grade 4) bleeding.

8.2.6.9 *Arterial Thromboembolic Events*

Serious, sometimes fatal, arterial thromboembolic events (ATEs), including myocardial infarction, cardiac arrest, cerebrovascular accident, and cerebral ischemia, occurred across clinical trials. Permanently discontinue ramucirumab in patients who experience an ATE.

8.2.6.10 *Peripheral neuropathy*

Participants with a known history of peripheral neuropathies and/or patients having received medications known to cause peripheral neuropathies (eg, prior antitubulin, platinum and/or taxanes) are at high risk of developing neuropathy. Peripheral neuropathies potentially present as signs and symptoms of sensory (paresthesia, dysesthesias, pain, and change in proprioception), motor (weakness), and neural dysfunctions.

There is no further recommendation beyond routine guidance on prevention and treatment of peripheral neuropathy. Cycle delays or modifications should be compliant with Appendix 4 ([Section 10.4](#)).

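### Protocol E27 cites coagulation limits in the inclusion criteria that are not there, so a numeric INR/PT/aPTT limit binds only participants on prophylactic anticoagulation

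*Protocol*

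**What the plan says.** The relevant text is in the protocol.

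- **E27, first sentence (Section 5.2)** excludes "Current therapeutic anticoagulation with warfarin, low-molecular-weight heparin, or similar agents".
- **E27, second sentence** makes an exception for low-dose prophylaxis: "Patients receiving prophylactic, low-dose anticoagulation therapy are eligible provided that the coagulation parameters defined in the inclusion criteria" are met. The brackets that follow give the limits: INR at most 1.5 or PT at most 1.5 times the upper limit of normal (ULN), and PTT/aPTT at most 1.5 times ULN.
- **Section 5.1** opens with "Participants are eligible to be included in the study only if all the following criteria apply" and lists I01 to I09.
- **E29 (Section 5.2)** sets the laboratory exclusions, introduced as "Poor organ function as defined by any one of the following prior to IMP administration".
- **Flow charts, Sections 1.3.1 and 1.3.2**, schedule coagulation tests within 7 days before the first infusion, at each cycle and at end of treatment. Footnote i defines them: "Coagulation: International normalized ratio (INR), aPTT".
- **Section 8.2.6.8** gives the clinical background: "Ramucirumab is an antiangiogenic therapy and has the potential to increase the risk of severe bleeding". It requires permanent discontinuation of ramucirumab after Grade 3 or 4 bleeding.
- **Section 5** forbids waivers of the enrolment criteria.

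**The concern.** E27 presents its limits as ones already set for entry to the study. If that general criterion is absent, the numbers in brackets bind only the participants named in the same sentence, those on prophylactic low-dose anticoagulation. The rule then works the wrong way round. The group whose coagulation is being altered on purpose has a ceiling, and a participant with an unexplained abnormality has none.

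Two things are at stake. One is safety at entry, for a drug with a stated bleeding risk. The other is consistent screening: one site may read E27 as evidence of a general limit and exclude accordingly, while another applies the limit only to participants on prophylaxis. Because waivers are not allowed, the criteria have to be usable exactly as written.

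**Working it through.** No sample size, error rate or event count depends on this, so the check is a search of each place where a coagulation limit for entry or dosing could sit.

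| Place (protocol) | What it covers | INR, PT or aPTT limit? |
|---|---|---|
| 5.1, I01 to I09 | age, histology, progression, genotype, CEACAM5, measurable lesion, ECOG, sex/contraception, consent | none (0 of 9) |
| 5.2, E27 | anticoagulation | yes, within the prophylaxis sentence only |
| 5.2, E29 a) to c) | creatinine/eGFR, bilirubin, AST/ALT/ALP, neutrophils, platelets, hemoglobin | none |
| 1.3.1 and 1.3.2, footnotes b and c | investigator review of baseline results; abnormal baseline tests repeated within 2 days of first dose | no cut-off |
| 6.6.3 | retreatment conditions | none |
| 8.2.5 and Appendix 2, Table 18 | test list and frequency | no cut-off |

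The inclusion criteria are numbered without a gap, so text removed from the public version does not explain the missing item.

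Two illustrative participants, identical in other respects, show the effect. The INR values are chosen for the example and do not come from the protocol.

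1. Participant A takes low-dose prophylactic heparin and has INR 1.6. E27 accepts either INR or PT for this limb, so assume PT does not meet its limit either. Since 1.6 > 1.5, A fails E27 and is excluded.
2. Participant B takes no anticoagulant and has INR 2.5, with bilirubin, transaminases, platelets and all other E29 values within limits. E27 does not reach B, and neither I01 to I09 nor E29 tests INR. B breaches no numeric criterion.

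B can be kept out only by E16, if the finding amounts to a significant bleeding disorder, or by judgement under E02 (significant concomitant illness) or E33 (unsuitable in the investigator's opinion).

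Other risks relevant to ramucirumab do have entry numbers for all participants: blood pressure (E13), proteinuria (E30), volume of hemoptysis (E10) and platelets (E29 c). Coagulation is measured for everyone but limited for one subgroup.

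**The case against.** The best defence is that the gap is narrow and that other provisions cover much of it.

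- Therapeutic anticoagulation is excluded outright by E27's first sentence, and significant bleeding disorders by E16. E02 and E33 are binding even though they carry no number.
- Baseline results must be reviewed by the investigator before treatment, and abnormal coagulation results are to be repeated. They are not ignored.
- Many participants with an INR raised by liver disease would fail E29 b), which excludes total bilirubin above 1.0 times ULN and limits AST, ALT and ALP, or E04, which excludes active hepatitis.
- The limits are printed in E27, so a site can apply that sentence despite the faulty reference.

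All of this stands, and it rules out a reading that may tempt: that anyone not on prophylaxis with deranged coagulation can receive ramucirumab. The text does not go that far. What survives is that none of these provisions supplies a number, and that an isolated INR or aPTT abnormality without a significant bleeding disorder passes every numeric test.

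A reader might also infer that bleeding from pre-existing coagulopathy would distort the DLT run-in. The documents support this poorly. The bleeding item in Table 5 requires Grade 3 or higher thrombocytopenia, which a raised INR or aPTT is not. Section 4.1 excludes events obviously unrelated to study drug, and the Study Committee confirms DLTs. A Grade 4 non-hematologic bleed remains a possible route, but that is not a basis for this point.

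Finally, it is tempting to say the authors meant the limits for everyone. The cross-reference is consistent with that, but it could equally be leftover wording. Nothing in the documents settles it.

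**Conclusion.** The defect is confirmed. E27 depends on coagulation parameters that neither Section 5.1 nor E29 contains, and the only numeric limit is tied to prophylactic low-dose anticoagulation. For participants on no anticoagulant, exclusion rests on E16 or on judgement. This is an operative eligibility rule that does not work as written, so it is more than a clerical slip.

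Its size cannot be put as a count. It would be wrong to say that every participant off prophylaxis is affected: only those with an abnormal INR or aPTT and no other ground for exclusion are, and the documents give no frequency for them. The practical reach of a correction is mainly the triplet cohort, planned at 6 to 12 DLT-evaluable participants. SAP Section 1.1 says that cohort had not started, whereas protocol Section 4.3 already draws on experience from the doublet cohort.

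The conclusion assumes that sites apply the criteria as printed and that no separate screening instruction outside these documents supplies a general limit.

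**What to change.** Before the triplet cohort enrols, reconcile E27 with Section 5.1 and E29 by stating to whom the limits printed in E27 apply.

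- If they apply to all participants, place them in the general criteria and make E27 refer to that item.
- If they apply only to participants on prophylactic anticoagulation, delete the reference to the inclusion criteria so that E27 stands alone.

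Which of the two is intended is a clinical decision for the sponsor, and this review takes no view on it or on the cut-offs.

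The cost is a short text amendment; INR and aPTT are already scheduled at screening. The first option might add some screen failures. Section 9.2 assumes 79% prescreening failure and 23% screening failure for the triplet cohort, so each prescreened person has a 0.21 × 0.77 = 0.162 chance of entering (74 × 0.162 = 12.0, matching the plan). Replacing one participant lost at screening would therefore take about 1/0.162 = 6.2 further prescreened people. The documents do not show how many such losses to expect.
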